11.2.1 Significance Level and Confidence Interval

All statistical tests will be two-sided and evaluated at a 5% level of significance.

11.2.2 Criteria for Equivalence

Equivalence will be determined based on the change from baseline in BCVA at Month 12. An equivalence margin of 4 letters will be used. If the 90%[#] (2-sided) confidence interval for the difference in means in change from baseline at month 12 is wholly within the equivalence margin (-4, 4), then the null hypothesis

$$H_0: \mu_1 - \mu_2 \leq -4 \text{ or } \mu_1 - \mu_2 \geq 4$$

will be rejected in favor of the alternative hypothesis

$$H_A: |\mu_1 - \mu_2| < 4,$$

where μ_1 represents the population mean change from baseline for patients treated with LUBT010, and μ_2 represents the population mean change from baseline for patients treated with Lucentis[®]. (# As generally required by US Food and Drug Administration [FDA])

Similar methodology will be used with 95%^{##} CI for difference. Thus, if 95% (2-sided) confidence interval, lies wholly within the equivalence margin (-4, 4), then the null hypothesis will be rejected. (## As generally required by the European Medicines Agency [EMA].)

11.3 Handling of Missing Data

There are many possible reasons for missing data (eg, patient refusal to continue in the study, treatment failures and successes, adverse events etc.), not all of which are related to the IP. Different degrees of data incompleteness can occur i.e. measurements may be available only at baseline or may be missed for one or several follow-up assessments. Such missing data will be handled by using appropriate methods. These methodologies will be described in detail in the SAP.

11.4 Patient Disposition

A detailed description of the patient disposition will be provided in the clinical study report. It will include the number of patients screened, randomized, completed, as well as the number of dropouts, with reasons for discontinuation and major protocol deviations. All patients entered in the study will be accounted for this.

11.5 Baseline and Demographic Characteristics

Categorical data will be summarized as frequencies, percentages and continuous data as descriptive statistics (number of patients, mean, SD, median, minimum value, and maximum value). Demographic data will include age, gender, race, ethnicity, weight, and disease specific baseline characteristics that will be detailed in SAP.

11.6 Analysis Sets

The analysis sets are described below.

11.6.1 Full Analysis Set (FAS)

The Full Analysis Set (FAS) will consist of all randomized patients who have received at least one dose of study drug with a baseline and one post baseline BCVA measurement. The FAS will be the primary population for analysis.

11.6.2 Per Protocol Analysis Set (PPS)

The Per Protocol Analysis Set will include all patients in the FAS without any major protocol deviation.

11.6.3 Safety Analysis Set (SAF)

Safety Analysis Set will include all patients who receive at least one dose of study medication. SAF will be used for all safety analyses.

11.6.4 Immunogenicity Analysis Set (IGS)

The immunogenicity analysis set (IGS) will include all patients who receive at least one dose of study medication and subsequently provide a valid post-baseline immunogenicity result.

11.7 Efficacy Analysis

11.7.1 Primary Efficacy Endpoint

The primary endpoint is mean change in BCVA from baseline in the study eye at the end of 12 months, assessed with the ETDRS chart.

The primary endpoint will be analyzed using ANCOVA model with fixed-effect treatment, and baseline BCVA as covariate.

Denote the population parameter for the mean change from baseline in BCVA by θ_R for LUBT010 arm, and by θ_L for Lucentis® arm, expressed in letters. The hypothesis to be tested will be

$$H_0: \theta_R - \theta_L \leq -4 \text{ or } 4 \leq \theta_R - \theta_L \text{ versus } H_A: -4 < \theta_R - \theta_L < 4.$$

The hypothesis will be tested using the two-sided 90% confidence interval for the difference as accepted by US FDA. If the 90% confidence interval lies wholly between -4 and 4, then the

null hypothesis will be rejected. The confidence interval will be constructed using a two-sample t-test.

Similar methodology will be used with 95% CI of mean difference for EMA. Thus, if 95% (2-sided) confidence interval, lies wholly within the equivalence margin (-4, 4), then the null hypothesis will be rejected.

Missing data in the primary endpoint will be imputed by multiple imputation approach under the assumption of outcome is Missing At Random (MAR). The MAR assumption will be implemented using ANCOVA model by repeated imputation of missing values in primary endpoint. For this assumption, missing outcomes are modeled using observations from a patient's own treatment arm. Thus, MAR would tend to reflect in the missing data any observed differences between treatment groups and is appropriately conservative for the objective of assessing equivalence. Then, to assess the robustness of MAR assumption in primary analysis, the sensitivity analysis via tipping point approach under the Missing Not At Random (MNAR) assumption will be performed.

Details will be provided in the SAP, which will be finalized and signed prior to database lock and unblinding

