Study Endpoints: Primary Endpoint: Mean change in BCVA from baseline in the study eye at the end of 12 months, assessed with the ETDRS chart. Secondary Endpoints: Efficacy: 
• Mean change in BCVA from baseline in the study eye at the end of 3 months assessed with the ETDRS chart.• Mean change in BCVA from baseline in the study eye at the end of 6 and 9 months, assessed with the ETDRS chart. Safety: 
• Adverse Events (AE) assessment, ocular and non-ocular• Ophthalmic examination• Physical and systemic examination• Vital signs• Electrocardiogram (ECG)• Laboratory parameters: Blood (hematology and biochemistry) and urinalysis Immunogenicity: Proportion of patients with anti-drug antibodies at the end of 1, 3, 6, 9, and 12 months. Exploratory Endpoint: 
• Mean change from baseline in National Eye Institute Visual Functioning Questionnaire – 25 (NEI-VFQ-25) Version 2000 (interviewer administered) scores at 3, 6, and 12 months. Statistical Methods: The primary endpoint of change in BCVA from baseline in the study eye at the end of 12 months will be analyzed using ANCOVA model with treatment as fixed_effect, and baseline BCVA as covariate. The equivalence of efficacy will be assessed based on 90%# (two-sided) confidence interval for the difference in mean change in BCVA from baseline in the study eye at end of 12 months, with an equivalence margin of 4 letters. (# As generally required by US Food and Drug Administration [FDA]) Similarly, the equivalence of efficacy will be assessed based on 95%## confidence interval of the difference in mean change in BCVA from baseline in the study eye at the end of 12 months, with an equivalence margin of 4 letters. (## As generally required by the European Medicines Agency [EMA].) For continuous data, summary statistics will include the number, arithmetic mean, standard deviation (SD), median, minimum, and maximum. For categorical data, frequency and percentage will be presented. The safety data and immunogenicity data will be summarized and listed.		

Table 1: Schedule of Assessment

Mon=Months d=day Rand=Randomization	Screening Period		Treatment & Assessment Period (12 months)													EOS/ Early Discontinuation
	Screening Visit	Rand	Safety Visit	1 mon @	2 mon @	3 mon @	4 mon @	5 mon @	6 mon @	7 mon @	8 mon @	9 mon @	10 mon @	11 mon @ (EOT)	12 mon ²¹ (EOS)	

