6 INVESTIGATIONAL PLAN

6.1 Overall Study Design and Plan

This is a global, Phase III, double blind, randomized, controlled clinical study. The objective of the study is to compare the efficacy, safety and immunogenicity of LUBT010 to that of Lucentis® in patients with neovascular AMD.

Approximately 75 –100 sites across Europe, US, and India, having ophthalmologists who are experienced in diagnosing and treating neovascular AMD, and where adequate facilities for conduct of trial are available will be selected for the study. Study will be initiated only after receipt of regulatory and EC approval. Screening investigations on patient will be done only after signing of written informed consent. Adequate number of patients will be screened to randomize approximately 600 patients to have 558 evaluable patients in the study. (Note: Every attempt will be made to ensure at least 25% of patients enrolled are with light colored irises).

Patients will be randomized on Day 1. Total 12 injections (Lucentis® or LUBT010 0.5 mg intravitreal injection, once monthly) would be given to each patient during the study. The duration of the treatment and assessments will be 12 months during which the efficacy, safety and immunogenicity assessments will be done. The total study duration for each patient would be around 13 months. It would include up to 28 days of screening period and 12 months of treatment and assessment period.

The trial consists of following parts:

- Screening Period (maximum 28 days)
- Treatment and Assessment Period (12 months)
 - Day 1 (Randomization and first dose of ranibizumab)
 - Safety Visit: Day 2 to 9 (on any day from Day 2 to Day 9)
 - Treatment visits (\pm 2 days): Day 31 (second dose), and thereafter monthly for a total of 12 months (i.e. Day 61, Day 91, Day 121, Day 151, Day 181, Day 211, Day 241, Day 271, Day 301, and Day 331) followed by post-injection visit/Telephonic Follow-Up, as deemed necessary by Investigator.
 - Day 360 (\pm 2 days) - End of Study (EOS)

After signing the informed consent form, the patients will undergo screening assessments to confirm eligibility. These include demographics, medical and surgical history, (including ophthalmic history), weight, ECG, vital signs, physical, systemic and ophthalmic examination, and laboratory assessments (blood and urine) as given in Table 1.

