7.1.3 Randomization of Study Treatments

The treatment arm (test or reference) for each patient during the study will be assigned according to randomization list. This randomization list will be prepared reviewed and finalized in a blinded manner and will not be accessible to the study team involved in the study conduct. The treatment will be assigned at the time of randomization, after confirming patient's

eligibility. Patients will be randomized in a 1:1 ratio to either LUBT010 or Lucentis®. Patients who qualify for study randomization will have a unique randomization number. Randomization will be stratified by iris color (light colored, not light colored) to maintain treatment balance within strata. Randomization block size will be specified in the randomization plan and will not be shared with investigators. After completion of required number (600 patients), some patients who qualify in screening may not be enrolled in the study.

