11 STATISTICAL EVALUATION

11.1 Sample Size and Power

Sample Size for Change from Baseline in BCVA at Month 12 (Primary Endpoint)

In order to determine the margin for equivalence, a meta-analysis based on current literature in AMD patients was performed. Data included were data from the 0.5 mg ranibizumab and the SHAM treatment groups. Studies included were in the original regulatory filing. Change from baseline to Month 12 of BCVA was used as the endpoint. A mean difference of 17.9 letters [95% CI 15.7-20.0] was found. Heterogeneity was assessed and was not found to be statistically significant ($p=0.5752$), and hence the fixed-effect model was used to construct the confidence interval. Based on a lower confidence bound of 15.7 letters, an equivalence margin of 4 letters preserved 74.5% of the treatment effect. The pooled standard deviation (SD) from the ranibizumab arms is 14.5 letters.

Figure 2: Meta-Analysis

A sample size of 558 evaluable patients allocated in 1:1 ratio (279 per treatment) at (two-sided) 5% level of significance and 80% power will be required to test the therapeutic equivalence between Lupin's LUBT010 verses Lucentis® at equivalence margin of 4 letters and SD of 14.5 letters.

Sample Size

Assuming a dropout rate of 7%, 600 patients will be randomized so as get approximately 558 evaluable patients in a 1:1 ratio between the two treatment arms (279 in each arm) to yield 80% power for the mean change from baseline in BCVA at the end of 12 months.

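### Randomization is stratified by iris colour, but the primary ANCOVA omits it and the deciding interval comes from a two-sample t-test that uses no covariate; the cost is small and conservative, and easily removed

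*Combined protocol and SAP*

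**What the plan says.** Section 7.1.3 states: "Randomization will be stratified by iris color (light colored, not light colored) to maintain treatment balance within strata". Section 6.1 adds a recruitment aim for the same factor: "Every attempt will be made to ensure at least 25% of patients enrolled are with light colored irises".

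The primary model appears twice, and neither statement has an iris-colour term. The synopsis (Statistical Methods) says the endpoint "will be analyzed using ANCOVA model with treatment as fixed_effect, and baseline BCVA as covariate". Section 11.7.1 says "The primary endpoint will be analyzed using ANCOVA model with fixed-effect treatment, and baseline BCVA as covariate".

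Section 11.7.1 bases the decision on intervals at two levels: "The hypothesis will be tested using the two-sided 90% confidence interval for the difference as accepted by US FDA" and "Similar methodology will be used with 95% CI of mean difference for EMA". On how the interval is formed it says only "The confidence interval will be constructed using a two-sample t-test".

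Missing outcomes are to be multiply imputed through an ANCOVA model fitted within the patient's own arm, followed by a tipping-point analysis. No covariates are listed for either. Section 11.7.1 leaves details to a SAP to be signed before database lock. The text supplied contains no SAP passage that adds iris colour or chooses between the ANCOVA and the t-test.

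**The concern.** Stratification balances iris colour between the arms. If the analysis then ignores the factor, any variation in BCVA change between strata stays in the error term, although it can no longer contribute to the difference between arms. The standard error is then slightly too large for the design, and the interval slightly too wide.

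The t-test sentence adds a second problem. A two-sample t interval has no covariates, so it also drops baseline BCVA, which the plan itself chose as its covariate. While that sentence stands, adding iris colour to the ANCOVA would leave the interval that decides equivalence unchanged. The two edits therefore belong together.

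What is at stake is precision in a trial planned at about 80% power, and an unambiguous rule fixed before unblinding. The validity of an equivalence claim is not in question.

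**Working it through.** **Inputs from the plan (section 11.1).** 279 evaluable patients per arm, SD 14.5 letters, margin 4 letters, 80% power at two-sided 5%, 7% dropout.

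**Assumptions.** True difference 0 (none is stated). Light-iris share p = 25%, the target floor in section 6.1, with 50% as an upper check. Difference in mean BCVA change between iris strata d = 0 to 5 letters. Iris colour independent of baseline BCVA. Complete data.

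**1. Reproduce the plan's sample size.** For two one-sided tests at 0.025 each (the 95% interval), n per arm = 2 × [14.5 × (1.960 + 1.282) / 4]² = 276.1, so 277. The exact t-based calculation gives 278. The plan's 279 gives 80.4% power, and 558 / 0.93 = 600 randomized. The 90% interval would need 226 per arm and has 89.2% power at 279. The sample size was therefore set on the 95% interval with an unadjusted SD, and it reproduces.

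**2. Half-width without any covariate.** SE = 14.5 × √(2/279) = 1.228. The 95% half-width is 1.964 × 1.228 = 2.411 and the 90% half-width is 1.648 × 1.228 = 2.023.

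**3. Half-width with iris colour.** Residual variance = 14.5² − d² × p(1 − p), with one fewer degree of freedom (555). At p = 25% and d = 5, 25 × 0.1875 = 4.69, which is 2.23% of 210.25. The residual SD is 14.34.

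**4. Power on a like-for-like basis.** Under stratified randomization the unadjusted estimate already has the smaller variance, and only its estimated SE is too large. So power without the term also rises a little with d.

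| Light share | d (letters) | Variance explained | 95% half-width with term | 95% CI power, without → with term |
|---|---|---|---|---|
| 25% | 0 | 0% | 2.411 | 80.39% → 80.39% |
| 25% | 2 | 0.36% | 2.407 | 80.47% → 80.59% |
| 25% | 3 | 0.80% | 2.402 | 80.56% → 80.84% |
| 25% | 5 | 2.23% | 2.384 | 80.89% → 81.63% |
| 50% | 5 | 2.97% | 2.375 | 81.05% → 82.04% |

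For the 90% interval at 25% and d = 5, the half-width goes from 2.023 to 2.000 and power from 89.6% to 90.0%.

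**5. False-equivalence rate.** At a true difference of 4 letters, p = 25% and d = 5, omitting the term gives 2.4% (95% interval) and 4.8% (90% interval), against nominal 2.5% and 5%. The error is on the conservative side.

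**6. The t-test sentence.** Suppose baseline BCVA correlates 0.3 with change (assumed). The residual variance is 210.25 × (1 − 0.09) = 191.3. The 95% half-width is 2.411 from the t-test, 2.300 from the ANCOVA, and 2.272 from the ANCOVA plus iris colour at d = 5. With no iris effect, taking the interval from the ANCOVA raises power from 80.4% to 85.3%. At d = 5, adding iris colour to the ANCOVA raises it from 85.8% to 86.4%.

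**7. Simulation check (40,000 runs, d = 5).** Power by t-test, ANCOVA, and ANCOVA plus iris colour was 81.1%, 81.0% and 81.7% at correlation 0, and 80.8%, 85.6% and 86.4% at correlation 0.3. False equivalence for the 95% interval at a true difference of 4 and correlation 0.3 was 2.32%, 2.32% and 2.46%. This agrees with the formulas.

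**The case against.** The strongest reply is that nothing fails. The planned size gives 80.4% power on the 95% interval without the term, the omission is neutral or conservative, and the documents do not show that iris colour predicts BCVA response. Section 3.1 links light eyes to the risk of AMD, not to the response to treatment. The upper end of the assumed range, 5 letters, exceeds the equivalence margin itself; at d = 2 the gain is 0.12 power points. All of this stands, and it is why the point is optional.

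Three further points stand in part.

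- The 25% share is a floor, so 0.7 power points is not a ceiling. At 50% light irises the gain is 1.0 point and 0.036 letters, which is still small.
- The calculations assume complete data. With 7% dropout and imputation, exact balance within strata is not guaranteed among the observed patients, so the statements on bias and error rate are not tested for that case.
- The conflict between ANCOVA and t-test is the larger matter and does not depend on stratification. It is treated here because the iris-colour edit has no effect on the decision until it is settled.

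The deferral to a SAP answers the complaint about unlisted imputation covariates only in part. It does not answer the rest, because the protocol already states a model and an interval method.

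**Conclusion.** The concern holds as a minor efficiency point. The stated analysis does not reflect the stratified randomization, and the deciding interval, read literally, uses no covariate.

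For iris colour alone, with 25% light irises and a stratum difference of 0 to 5 letters, the loss is 0 to 0.03 letters of 95% half-width and 0 to 0.7 points of power. It is nil if iris colour is not prognostic. With complete data there is no bias and no increase in false equivalence. The t-test sentence costs more if baseline BCVA is prognostic: about 0.11 letters of half-width (2.411 − 2.300) at an assumed correlation of 0.3. Both sizes rest on assumed effects, because the documents give neither. The planned sample size is unaffected.

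**What to change.** Before unblinding:

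1. Add iris colour (light / not light) as a fixed effect in the primary ANCOVA, in the synopsis and in section 11.7.1.
2. Replace the t-test sentence in section 11.7.1 with a statement that both the 90% and 95% intervals come from the ANCOVA-adjusted treatment difference, pooled over the multiple imputations.
3. Name iris colour as a covariate in the imputation model and in the tipping-point analysis.
4. If iris colour is to stay out, state the reason.

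The statistical cost is one of about 555 degrees of freedom; at d = 0 the half-width is unchanged to three decimals. No new data are needed, since iris colour is already recorded for stratification. The administrative cost is the wording change, with whatever approvals section 13.3 requires, and the SAP should carry the same text.

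### The interval that decides equivalence is defined in two ways: from an ANCOVA with baseline BCVA, and from a two-sample t-test that takes no covariate

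*Combined protocol and SAP*

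**What the plan says.** Section 11.7.1 sets the model first: "The primary endpoint will be analyzed using ANCOVA model with fixed-effect treatment, and baseline BCVA as covariate". It then gives the hypotheses with a margin of 4 letters and the decision rule: "The hypothesis will be tested using the two-sided 90% confidence interval for the difference as accepted by US FDA". The construction of that interval follows: "The confidence interval will be constructed using a two-sample t-test". The EMA interval inherits it: "Similar methodology will be used with 95% CI of mean difference for EMA". Later in the section ANCOVA appears again, for imputation: "The MAR assumption will be implemented using ANCOVA model by repeated imputation of missing values in primary endpoint".

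Elsewhere:
- The synopsis (Statistical Methods) says the primary endpoint "will be analyzed using ANCOVA model with treatment as fixed_effect, and baseline BCVA as covariate" and goes straight on to the 90% and 95% interval rules. It mentions no t-test.
- Section 11.2.2 requires the interval for the difference in mean change to lie inside (-4, 4) and names no method.
- Section 11.1 sizes the trial on an unadjusted SD: "The pooled standard deviation (SD) from the ranibizumab arms is 14.5 letters".
- Sections 11.2 and 11.7.1 defer detail to a SAP to be finalized before database lock; 11.7.1 adds that it will be signed before unblinding. The document supplied contains no separate SAP text.

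**The concern.** An equivalence trial is decided by whether one interval lies inside the margin, so the method that produces the interval is the primary analysis in practice. A two-sample t-test estimates the raw difference in mean change. The ANCOVA estimates that difference after correcting for chance imbalance in baseline BCVA, with a smaller residual SD if baseline predicts change. Taken literally, 11.7.1 fits the ANCOVA but does not use it for the interval that decides, and this applies to both the FDA and the EMA decision.

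Two things are at stake. The decision rule can be read in two ways, and a result near the margin could pass under one and fail under the other. The t-test reading also forgoes whatever precision the named covariate offers.

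**Working it through.** **Inputs.** From section 11.1: 279 evaluable per arm, SD 14.5 letters, margin 4 letters, two-sided 5%, 80% power, 7% dropout. From 11.7.1: 90% and 95% two-sided intervals. Not in the documents: the true difference (taken as 0 unless stated) and the correlation rho between baseline BCVA and change (assumed 0.2 to 0.4 in absolute value, with smaller values also shown).

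**1. Reproduce the plan's sample size.** For two one-sided tests with true difference 0, the normal approximation is n per arm = 2 × [SD × (z(1−α) + z(1−β/2)) / margin]².
- 95% interval (α = 0.025 per side, β = 0.20): 2 × [14.5 × (1.960 + 1.282) / 4]² = 276.1, so 277 per arm. The t-based version needs 278, and 279 per arm gives 80.4% power.
- 90% interval (α = 0.05 per side): 225.1, so 226 per arm, which does not match the plan.
- Dropout: 558 / (1 − 0.07) = 600.

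The stated 558 and 600 therefore reproduce for the 95% interval with an unadjusted SD.

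**2. Unadjusted (t-test) interval.** SE = 14.5 × √(2/279) = 1.228 letters. Half-width = t × SE with 556 degrees of freedom:
- 95%: 1.964 × 1.228 = 2.41 letters, power 80.4%.
- 90%: 1.648 × 1.228 = 2.02 letters, power 89.2%.

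**3. ANCOVA interval.** The residual SD is 14.5 × √(1 − rho²), with 555 degrees of freedom.

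| abs. rho | Residual SD | 95% half-width | Power, 95% CI | 90% half-width | Power, 90% CI |
|---|---|---|---|---|---|
| 0.2 | 14.21 | 2.36 | 82.6% | 1.98 | 90.6% |
| 0.3 | 13.83 | 2.30 | 85.3% | 1.93 | 92.3% |
| 0.4 | 13.29 | 2.21 | 88.8% | 1.85 | 94.3% |

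**4. Gap between the two point estimates.** It has SD of about |rho| × 1.228, that is 0.25, 0.37 and 0.49 letters for the three values. The simulated median absolute gap is 0.16, 0.24 and 0.33 letters.

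**5. How often the verdicts differ.** Simulation of 40,000 trials per rho, complete data, baseline and change bivariate normal, true difference 0, both intervals computed on the same data:

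| abs. rho | Opposite verdicts, 95% CI | ANCOVA only succeeds, 95% | t-test only succeeds, 95% | Opposite verdicts, 90% CI |
|---|---|---|---|---|
| 0.2 | 5.6% | 3.9% | 1.7% | 3.7% |
| 0.3 | 8.6% | 6.8% | 1.8% | 5.3% |
| 0.4 | 11.8% | 10.3% | 1.6% | 7.0% |

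Rows add up to rounding. The Monte Carlo standard error of the 11.8% is about 0.16 percentage points. With 20,000 trials at rho 0.1, the verdicts differ in 2.9% (95%) and 1.9% (90%) of trials. Smaller runs (4,000 trials per scenario, rho 0.2 to 0.4) at non-zero true differences give about 7% to 14% (95%) and 5% to 11% (90%) at 1 letter, and about 6% to 14% and 7% to 14% at 2 letters.

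**The case against.** The strongest reply is that the documents lean one way. ANCOVA is the stated model in both the synopsis and 11.7.1, and the t-test sentence may be loose wording for a t-based interval on the ANCOVA treatment contrast, or for two one-sided tests. That may be what was meant, but the text does not say so, and the sentence is the only one that says how the interval is built.

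Second, section 11.2 lets the SAP record departures from the protocol. If the SAP settles the point before unblinding, nobody can choose the interval after seeing results by arm. This is fair and limits the harm. It does not remove the contradiction, because a SAP that names either method must depart from one of the two protocol statements.

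Third, an unadjusted interval is valid and matches the sample-size basis, so preferring ANCOVA for precision does not show an error. That also stands: at rho 0.2 the gain is only 0.05 letters of half-width. The point rests on the inconsistency, with precision as a secondary reason for resolving it towards ANCOVA.

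Fourth, the size depends on an assumed rho. At rho 0.1 the disagreement is under 3%, and the simulations use complete data where the plan uses multiple imputation.

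**Conclusion.** The concern holds. Section 11.7.1 gives two incompatible constructions for the interval that decides equivalence, and nothing in the supplied document says which governs. Validity, error rate and sample size are sound under either reading, so this is a specification fault that should be corrected before unblinding, not a threat to the design.

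Its size depends on how well baseline BCVA predicts change. With an absolute correlation of 0.2 to 0.4 and no true difference, the choice of method reverses the verdict in roughly 6% to 12% of trials at the 95% level and 4% to 7% at the 90% level. Most of these reversals are trials in which only ANCOVA shows equivalence. With a weaker correlation the figures shrink, but the ambiguity remains. The figures assume 279 complete cases per arm, SD 14.5 and normal data.

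**What to change.** In section 11.7.1, delete the t-test sentence. State instead that the 90% and 95% intervals compared with (-4, 4) are for the baseline-adjusted (least-squares mean) treatment difference from the primary ANCOVA, fitted to each imputed data set and combined by Rubin's rules. Add the same reference to section 11.2.2 so that the decision rule names its method, and carry it into the SAP before unblinding. If the unadjusted t-test interval is wanted, label it a sensitivity analysis with no role in the decision.

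The cost is a sentence of text. Baseline BCVA is already collected, so no extra patients, visits or data are needed, and the planned 558 evaluable patients remain sufficient.
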